## 1 Synopsis

Study-ID	04-Anlt-19
Title of the trial	Observational study to evaluate the EPI demiology of Surgical-induced Acute Kidney Injury
Acronym	EPIS-AKI
Responsible institution	Department of Anesthesiology, Intensive Care and Pain Medicine [name] [name]
Medical condition	Complications after surgery
Principle investigator	Univ.-[name]. med. [name] Department of Anesthesiology, Intensive Care and Pain Medicine University Hospital of Muenster [name] [name] [contact]; [contact]; Email: [contact]
Medical project management	[name]. med. [name] Department of Anesthesiology, Intensive Care and Pain Medicine University Hospital of Muenster [name] [name] [contact]; [contact]; Email: [contact]  Dr. med. [name] Department of Anesthesiology, Intensive Care and Pain Medicine; University Hospital of Muenster [name] [name] [contact]; [contact]; Email: [contact]
Study coordinator	Dr. oec. troph. [name] Department of Anesthesiology, Intensive Care and Pain Medicine; University Hospital of Muenster [name] [name] [contact]; [contact]; Email: [contact]
Trial type	International prospective, observational, multi-center, cross-sectional cohort study

Participating centers	This clinical trial will be carried out as an international multicenter observational cohort trial in Europe and the USA. If necessary, further qualified trial sites may be recruited to the trial. The listing of trial sites, principal investigators, sub-investigators, and further trial staff, will be kept and continuously updated in a separate list. The final version of this list will be attached to the final report of the clinical trial.
Biometry	Dr. rer. medic. [name], M. Sc. Institute of Biostatistics and Clinical Research University of Muenster [name] [name] [contact] Email: [contact]
Funding	Unrestricted research grant from Baxter
Objective(s)	
Acute kidney injury (AKI) is a severe clinical complication with increasing incidence and is associated with adverse short- and long-term outcomes resulting in a major health care burden worldwide. The introduction of consensus classification systems has enhanced the awareness for AKI. The evaluation of an accurate occurrence rate for AKI is of great importance for health policy, quality initiatives as well as for designing clinical trials. However, analyzing AKI from existing databases is often limited by missing data elements, especially the inclusion of the urine output criteria. Missing data and the use of different definitions before the consensus classification are the reasons for large variations in reported occurrences of surgical induced AKI.
 
The primary objective of the study is to prospectively evaluate the incidence of AKI within 72 h after extended surgical procedures that require admission to an observation unit (e.g., ICU, IMC, PACU) using the latest consensus definition for AKI (Kidney Disease: Improving Global Outcomes criteria) and a standardized data collection instrument.
 
Secondary objectives are:
 
 
• to evaluate the severity and duration of post-surgery AKI, as well as the use of renal replacement therapy (RRT), all-cause mortality (ICU and hospital), ICU and hospital length of stay, and the occurrence of MAKE (major adverse kidney events) up to 90 days after extended surgical procedures,
 
• to determine the effects of pre- and intraoperative factors on the occurrence of AKI,
 
• to determine the association between AKI and postoperative outcomes including use of RRT, all-cause mortality, ICU and hospital length of stay, the occurrence of MAKE (major adverse kidney events) and CKD (chronic kidney disease) development or progression up to 90 days after extended surgical
 

	
procedures,
 
 
• to determine the transition from non-AKI and AKI to CKD (i.e. development or progression; CKD defined by CKD-KDIGO) at day 90 after extended surgical procedures.
 

Key inclusion and exclusion criteria	
Inclusion criteria:
 
 
1. Age <math>\geq</math> 18 years
 
2. Major surgeries with a duration of at least 2 h
 
3. Planned or unplanned admission to the ICU, IMC or PACU after surgery
 
4. Written informed consent
 
 
Exclusion criteria:
 
 
1. Pre-existing AKI
 
2. AKI within the last 3 months
 
3. End stage renal disease with dialysis dependency
 
4. Kidney transplant
 

Study endpoints	
Primary endpoint: Occurrence of AKI within 72h after extended surgery according the KDIGO criteria.
 
Secondary endpoints: Secondary endpoints are:
 
 
• Use of renal replacement therapy
 
• Duration of AKI (transient vs. persistent)
 
• Length of ICU stay
 
• Length of hospital stay
 
• Survival 
 
◦ ICU mortality
 
◦ Hospital mortality
 
 
 
• MAKE90 (major adverse kidney events within 90 days): combined endpoint consisting of: 
 
◦ Mortality
 
◦ renal replacement therapy
 
◦ persistent renal dysfunction defined as serum-creatinine <math>\geq</math> 1.5 times as compared to baseline serum-creatinine
 
 
 
• Transition from non-AKI and AKI to CKD (i.e. development or progression; CKD defined by CKD-KDIGO) at day 90
 

Number of subjects	To be analyzed in the trial: n=10,000
Time plan	First patient first visit (FPFV): 01/06/2020 Last patient first visit (LPFV): 30/06/2022 Last patient last visit (LPLV): 30/09/2022 Final study report: 31/12/2022
Statistical analysis	
Statistical analyses will be performed according to the principles of the ICH-guideline E9 "Statistical Principles for Clinical Trials" using standard statistical software. Analyses will be performed based on the Full Analysis Set (FAS).
 
In the primary analysis the incidence of AKI will be estimated together with the exact corresponding two-sided 95% confidence interval according to Clopper-Pearson.

	
To detect factors that might be correlated to the occurrence of AKI (e.g., type/length of surgery, use of blood products, morbidities), exploratory uni- and multivariable logistic regression analyses will be conducted.
 
For secondary outcomes, descriptive statistics, point estimates and corresponding 95% confidence intervals will be derived.
 
To quantify evidence of differences between groups given by categorical parameters, such as the type of surgery, exploratory inferential analyses will be performed, using statistical tests like t-tests, Mann-Whitney-U tests, Kruskal-Wallis tests, Chi-square tests or Fisher's exact tests, appropriate to the distributional characteristics of the endpoint.
 
Additionally, subgroup analyses will be conducted based on the type of surgery to identify variables that are correlated with the occurrence of AKI in each group.

Power calculation	
The primary aim of the study is to estimate the incidence of post-surgery AKI and to derive the corresponding exact two-sided 95% confidence interval according to Clopper-Pearson. Depending on the type of surgery, AKI incidences of 1.8-39.3% are reported in existing literature. As the width of the confidence interval increases, the closer the observed incidence of post-surgery AKI equals 50%, a rate of 40% is assumed, as a conservative approach. Using this assumption, the width of the confidence interval based on a sample size of <math>n = 10,000</math> patients and a confidence level of 95% is given by 0.019. Thus, with <math>n = 10,000</math> patients, the incidence of post-surgery AKI can be estimated with at least this precision.
 
The study also aims to detect factors that might be correlated to the occurrence of post-surgery AKI, as e.g. the type of surgery (i.e. cardiac, neurological etc.) and predefined preoperative and intraoperative factors.
 
Therefore, further exploratory analyses such as uni- and multivariable logistic regression analyses will be conducted. Given the relatively large number of different types of surgeries, a sample size of <math>n = 10,000</math> patients is sufficient to investigate the influence of this parameters on the occurrence of post-surgery AKI in a uni- and multivariable context.

Trial registration	
The trial is registered at ClinicalTrials.gov (ClinicalTrials.gov Identifier: NCT04165369).

## 2 Abbreviations

ACE	Angiotensin Converting Enzyme
AKI	Acute Kidney Injury
APACHE	Acute Physiology And Chronic Health Evaluation
ARB	Angiotensin Receptor Blocker
ASA	American Society of Anesthesiologists
CKD	Chronic Kidney Disease
COPD	Chronic Obstructive Pulmonary Disease
EPIS-AKI	Epidemiology of Surgical-induced Acute Kidney Injury
FPFV	First patient first visit
GFR	Glomerular Filtration Rate
ICH	International Conference on Harmonisation of Technical Requirements
ICU	Intensive Care Unit
IMC	Intermediate Care
KDIGO	Kidney Disease: Improving Global Outcomes
LPFV	Last patient first visit
LPLV	Last patient last visit
MAKE	Major Adverse Kidney Events
NSAID	Nonsteroidal Anti-inflammatory Drug
NYHA	New York Heart Association
OD	Operative Day
PACU	Post Anesthesia Care Unit
POD	Postoperative day
RRT	Renal Replacement Therapy
SAPS	Simplified Acute Physiology Score
SAP	Statistical Analysis Plan
UO	Urine Output

## 3 General remarks

This SAP was written without knowledge of any study data.

## 4 Background of the study

Acute kidney injury (AKI) is a severe clinical complication with increasing incidence and it is associated with adverse short- and long-term outcomes resulting in a major health care burden worldwide. AKI is now being considered as independent risk factor for adverse outcomes. Since the introduction of consensus classification systems (Risk Injury Failure Loss and End stage [RIFLE], Acute Kidney Injury Network [AKIN], and the Kidney Disease: Improving Global Outcomes [KDIGO] criteria), the awareness for its importance has grown tremendously and most of the studies use these definitions to report AKI rates.

The establishment of an accurate occurrence rate for AKI is important for health policy, quality initiatives as well as for designing clinical trials. However, analyzing AKI from existing databases in the surgical setting is often limited by missing data elements needed for the application of these definitions, especially the inclusion of the urine output criteria. Additionally, administrative databases are limited since billing codes do not capture many cases of AKI. This might be one explanation for the large variation in occurrence rates of AKI reported in the surgical setting.

The objective of the epidemiology of Surgical-induced Acute Kidney Injury (EPIS-AKI) trial is to prospectively evaluate the epidemiology of AKI after extended surgical procedures in hospitals using the latest consensus definition for AKI and a standardized data collection instrument and to assess the dependence of AKI on preoperative and intraoperative factors (Study protocol, version 1.2, 29.06.2020).

## 5 Study objectives

### Primary objective:

The primary objective of the study is to evaluate the incidence of AKI within 72 h after extended surgical procedures that require admission to an observation unit (e.g., ICU, IMC, PACU) using the latest consensus definition for AKI (Kidney Disease: Improving Global Outcomes criteria).

### Secondary objectives:

The secondary objectives of the study are:

- to evaluate the severity and duration of post-surgery AKI, as well as the use of renal replacement therapy (RRT), all-cause mortality (ICU and hospital), ICU and hospital length of stay, and the occurrence of MAKE (major adverse kidney events) and CKD (chronic kidney disease) development or progression up to 90 days after extended surgical procedures,
- to determine the effects of pre- and intraoperative factors on the occurrence of AKI,
- to determine the association between AKI and postoperative outcomes including use of RRT, all-cause mortality, ICU and hospital length of stay, and the occurrence of MAKE up to 90 days after extended surgical procedures.
- Transition from non-AKI and AKI to CKD (i.e. development or progression; CKD defined by CKD-KDIGO) at day 90.

## 6 General study design and plan

The EPIS-AKI trial is an international, prospective, observational, multi-center, cross-sectional cohort study including patients that undergo extended surgical procedures.

[figure not shown]

Figure 1: Trial workflow.

Eligible patients, i.e. meeting all inclusion and none of the exclusion criteria, will be enrolled into the study (Figure 1). The visit plan is shown in Table 1.

Visit	S	B	OD	POD 1-3	Day 90
Inclusion and Exclusion criteria	X				
Demography Age, gender, race, height, weight, creatinine, comorbidities, ASA status, medication		X			
Admission diagnosis, source of admission		X			
Intraoperative data Surgical procedure (speciality, type, duration, if cardiac: CPB)			X		

/ aortic X-clamp duration), fluid status (fluid intake, transfusion, blood loss, urine output), use of cell saver, episodes of hypotension, drug application, intraoperative complications					
Postoperative data APACHE, SAPS, fluid status, drug application, postoperative complications				X	
AKI Stage, occurrence, duration, diagnosis, RRT				X	
Concomitant Medication Vasopressors, nephrotoxic agents, diuretics				X	
Mortality					X
Length of primary stay (ICU, Hospital)					X
Serum-creatinine					X
Renal recovery					X
Number of days of RRT/RRT dependence					X
MAKE (major adverse kidney events)					X

Abbreviations: S, Screening; B, Baseline, OD, operative day; POD, postoperative day; ASA, American Society of Anaesthesiology; CPB, cardiopulmonary bypass; APACHE, Acute Physiology And Chronic Health Evaluation; SAPS, Simplified Acute Physiology Score; AKI, Acute Kidney Injury; RRT, Renal Replacement Therapy; ICU, intensive care unit.

Table 1: Visit plan.

## 7 Inclusion and exclusion criteria

The inclusion and exclusion criteria of the study are:

### Inclusion criteria:

1. Age  $\geq$  18 years
2. Major elective or emergency surgery procedures with a duration of at least 2h
3. Planned or unplanned admission to the ICU, IMC or PACU after surgery
4. Informed Consent

Major surgeries will be targeted within the broad subgroup domains of neurosurgery, cardiac, vascular, gynecology, thoracic, urology, orthopedics/trauma and abdominal surgery.

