#### **11.3.5 Intraoperative data**

- Surgical specialty
- Type of surgery
- Duration of surgery
- If cardiopulmonary bypass (CPB): Total CPB time / Total X-Clamp time
- Intake of Crystalloids / Colloids / Erythrocytes (EC) / Thrombocytes (TC) / Fresh frozen plasma (FFP)
- Use of cell saver
- Total blood loss
- Use of urine catheter
- Total urine output
- Episodes of hypotension (MAP < 55 mmHg for more than 5 minutes)
- Application and type of vasopressors
- Application and type of nephrotoxic agents
- Application of diuretics
- Intraoperative complications / Type of complications

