### 12.3 Secondary analyses

All secondary analyses are considered exploratory.

Secondary outcomes (see 11.2) will be evaluated based on descriptive statistics, point estimates and corresponding 95% confidence intervals.

To detect factors that might be correlated to the occurrence of AKI, MAKE90, CKD90 (i.e. development or progression), and a persistent AKI, exploratory uni- and multivariable logistic regression analyses will be conducted (including age, arterial hypertension, diabetes mellitus, sex, type of surgery as explanatory variables).

The association between AKI (overall and by severity, duration) and postoperative outcomes including use of RRT, all-cause mortality, ICU and hospital length of stay, the occurrence of MAKE90, the development or progression of CKD90, and the estimated glomerular filtration rate (eGFR) at day 90 will be assessed descriptively. Subsequent analyses for related risk factors will be undertaken.

The impact of baseline serum-creatinine and urinary output on the occurrence of MAKE90 in patients with post-surgical AKI will be assessed by logistic regression analyses.

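### The SAP enrols elective and emergency surgery but does not list or model urgency, so the type-of-surgery odds ratios in section 12.3 may partly reflect emergency case mix

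*SAP*

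**What the plan says.** Inclusion criterion 2 in SAP section 7 reads "Major elective or emergency surgery procedures with a duration of at least 2h". The SAP mentions urgency of surgery nowhere else.

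- **Data collected (section 6, Table 1).** The surgical items begin "Surgical procedure (speciality, type, duration, if cardiac: CPB", followed by cross-clamp time and intraoperative data. At baseline the table also has "Admission diagnosis, source of admission". Neither row names elective or emergency status.
- **Variables for analysis (section 11.3).** Section 11.3.5 lists "Surgical specialty", then type of surgery and "Duration of surgery", with no item for urgency. ASA score is listed in 11.3.3, and APACHE II and SAPS in 11.3.6.
- **Models (section 12.3).** The stated purpose starts "To detect factors that might be correlated to the occurrence of AKI, MAKE" and extends to MAKE90, CKD90 and persistent AKI. The regressions are described as "including age, arterial hypertension, diabetes mellitus, sex, type of surgery as explanatory variables".
- **Meaning of type of surgery.** The synopsis writes "the type of surgery (i.e. cardiac, neurological etc", that is, the surgical field. Section 8 uses the term in the same way.
- **Subgroups (section 12.5).** These are defined by type of surgery only.

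All secondary analyses are declared exploratory.

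**The concern.** One of the secondary objectives in section 5 is to determine how pre- and intraoperative factors affect AKI. Whether an operation is elective or an emergency is settled before it starts and could plausibly affect AKI, death and MAKE90. The eight target domains in section 7 include orthopedics/trauma, so the emergency share may well differ between domains.

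Type of surgery is the only surgical term named in the models. A difference in emergency share would therefore tend to load on its coefficient, and a field with many emergencies could appear to carry more kidney risk than its operations do. Analysing each field separately, as section 12.5 plans, would not separate the two, because elective and emergency cases remain mixed within each field.

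There is also a reporting loss. One study behind Table 2 (reference 18, with rows of 9.7% and 3.1%) is limited by its title to elective noncardiac surgery. A pooled incidence cannot be compared cleanly with such figures unless it can be split by urgency.

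**Working it through.** **The plan's own figure.** The SAP's only design figure is the width of the exact 95% interval at a 40% AKI rate with n = 10,000, given as 0.019. Clopper-Pearson with 4,000 events in 10,000 gives 0.3904 to 0.4097, a width of 0.0193. The figure reproduces. It does not depend on urgency, and adding a covariate to the section 12.3 models would not change it.

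**Is urgency anywhere in the analysis plan?** The places where it could appear were compared:

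| Place in SAP | Surgical or admission items | Urgency? |
|---|---|---|
| Section 7, criterion 2 | elective or emergency | yes |
| Table 1 | speciality, type, duration, CPB; admission diagnosis and source | no |
| Sections 11.3.1 to 11.3.6 | specialty, type, duration and others | no |
| Section 12.3 models | type of surgery | no |
| Section 12.5 subgroups | type of surgery | no |

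**How far could the type-of-surgery odds ratio move?** The SAP gives neither an emergency share nor an effect of urgency, so the inputs are assumptions:

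- elective AKI risk *b* of 10 to 40% (the upper end is the section 8 planning rate, used here as the elective risk);
- emergency versus elective odds ratio *R* of 1.5 to 3;
- emergency share 5% in field A and 20 to 40% in field B;
- no true difference between fields, and the other four covariates unrelated to urgency and field.

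Formulas:

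- emergency risk: *e* = *bR* / (1 − *b* + *bR*);
- field risk with emergency share *s*: *p* = (1 − *s*)*b* + *s e*;
- odds ratio with urgency omitted: [*p*B/(1 − *p*B)] / [*p*A/(1 − *p*A)].

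Smallest case, *b* = 0.40, *R* = 1.5, shares 5% and 20%:

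- *e* = 0.60/1.20 = 0.50
- *p*A = 0.95 × 0.40 + 0.05 × 0.50 = 0.405
- *p*B = 0.80 × 0.40 + 0.20 × 0.50 = 0.420
- odds ratio = (0.420/0.580)/(0.405/0.595) = 1.06

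Middle case, *b* = 0.20, *R* = 2, shares 5% and 40%:

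- *e* = 0.40/1.20 = 0.333
- *p*A = 0.95 × 0.20 + 0.05 × 0.333 = 0.207
- *p*B = 0.60 × 0.20 + 0.40 × 0.333 = 0.253
- odds ratio = 1.30

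Largest case, *b* = 0.10, *R* = 3, shares 5% and 40%:

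- *e* = 0.30/1.20 = 0.25
- *p*A = 0.95 × 0.10 + 0.05 × 0.25 = 0.1075
- *p*B = 0.60 × 0.10 + 0.40 × 0.25 = 0.160
- odds ratio = (0.160/0.840)/(0.1075/0.8925) = 1.58

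The elective risk also matters. With shares of 5% and 30% and *R* = 3, the odds ratio is 1.41 at *b* = 0.10 but 1.31 at *b* = 0.40.

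With equal shares, *p*A = *p*B and the odds ratio is 1.00 for every *b* and *R*. With urgency in the model, the field odds ratio is 1.00 in all these cases, because the risks were built without a field effect.

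**The case against.** The strongest reply is that these models are exploratory and open. The word introducing the covariates in section 12.3 need not close the list. The synopsis mentions further factors by way of example, and sections 12.3 and 12.4 leave room for later analyses. An association between field and AKI that reflects case mix is a legitimate descriptive result, and urgency is only one of several covariates that could be wished for. This limits the weight of the point. It does not remove it: nothing in the SAP adds urgency, and section 5 speaks of effects of factors, not only of description.

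A second reply is that the protocol or case report form, which are not at hand, may record urgency. Table 1 also lists "Admission diagnosis, source of admission", and ASA score is collected. That may be so, and no claim is made that the data are missing. But none of these items is named in the models or designated as a measure of urgency, and collecting a variable does not put it in the analysis.

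A reader might also infer more than the documents support:

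- **That the comorbidity coefficients are biased.** Age and sex precede urgency, and hypertension and diabetes ordinarily do too. Urgency may lie on the path from comorbidity to AKI, in which case adjustment would remove part of the effect sought. No calculation here concerns those coefficients.
- **That the primary result is biased.** The pooled incidence in the enrolled population and its exact interval do not depend on the regression covariates.
- **That urgency is known for every patient.** Criterion 2 admits both kinds of operation and excludes neither, so a site can confirm eligibility without recording which applies. The synopsis version of the criterion does not mention urgency.

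**Conclusion.** The point holds for the type-of-surgery odds ratios in the section 12.3 models. The SAP admits both elective and emergency operations, then lists urgency in no analysis variable and names it in no model, leaving surgical field as the only surgical term. Those odds ratios will partly reflect urgency if two conditions hold: the emergency share differs between fields, and urgency affects the outcome.

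The SAP gives no data on either condition, so the size is unknown. Under the assumed inputs, an odds ratio that is truly 1.00 moves to about 1.06 to 1.58, and it does not move if the shares are equal. The illustration is for AKI. The same mechanism applies to MAKE90, CKD90 and persistent AKI, but no size was worked out for them. This is a worthwhile and inexpensive improvement to an exploratory analysis, with no consequence for the primary estimate or the sample size.

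**What to change.** 1. Add urgency of surgery (elective / emergency) to the variables in section 11.3.5. Take it from the case report form if it is recorded there; otherwise add one item.
2. In section 12.3, enter urgency beside type of surgery in the multivariable models for AKI, MAKE90, CKD90 and persistent AKI. Show the coefficients for hypertension and diabetes with and without urgency, since it may lie on their pathway.
3. Report AKI incidence with its exact 95% confidence interval separately for elective and emergency patients, as a supportive table. The pooled primary analysis in section 12.2 stays as it is.

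The cost is one extra parameter per model, one table and possibly one form item. With 10,000 patients planned, one binary term is a small burden on the models, and no design figure changes.
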